4.5.4.3 Missing data patterns

A summary of missing FPG as well as FPG data collected following rescue medication initiation or discontinuation study medication will be presented for the short-term period, as described in Section 4.4.2.3.

4.5.5 Comparison of mean reduction in FPG from baseline at Week 26 between the low-dose/high-dose treatment regimen and placebo

Data will be multiply imputed based on the same approach as described for the primary analysis in Section 4.4.1 at all scheduled time points up to and including Week 26, replacing HbA1c with FPG, and will include all data regardless of rescue medication initiation or adherence. Analysis will be performed by fitting the weighted ANCOVA model described in Section 4.1.9 (replacing HbA1c with FPG). The analysis model will be evaluated in each imputed data set and the results will be combined using Rubin's rules as described in Section 4.1.12.4. The weight matrix W_1 described in Section 4.1.9 for the comparison of the low-dose/high-dose treatment regimen versus placebo will be used for this analysis.

In addition, a line plot of LS mean \pm 95% confidence interval (CI) by visit up to Week 26 will be displayed.

4.5.5.1 Sensitivity analysis for secondary endpoint of mean reduction in FPG from baseline at Week 26 between the low-dose/high-dose treatment regimen and

placebo excluding data following rescue medication initiation/early treatment discontinuation

The above primary analysis (Section 4.5.5) for the comparison of mean reduction in FPG from baseline at Week 26 between the low-dose/high-dose treatment regimen and placebo will be repeated excluding data following rescue medication initiation or early treatment discontinuation but missing data will be imputed assuming MAR as described in Section 4.1.12.5. A weighted ANCOVA model will be used for this analysis.

4.5.6 Comparison of mean reduction in FPG from baseline at Week 26 between the low-dose treatment regimen and placebo

Data will be multiply imputed based on the same approach as described for the primary analysis of the primary endpoint in Section 4.4.1 at all scheduled time points up to and including Week 26, between the low-dose treatment regimen and placebo, replacing HbA1c with FPG, and will include all data regardless of rescue medication initiation or adherence. Analysis will be performed by fitting the weighted ANCOVA model described in Section 4.1.9 (replacing HbA1c with FPG). The weight matrix W2 described in Section 4.1.9 for the comparison of the low-dose treatment regimen versus placebo will be used for this analysis. The analysis model will be evaluated in each imputed data set and the results will be combined using Rubin's rules as described in Section 4.1.12.4.

4.5.6.1 Sensitivity analysis for secondary endpoint of mean reduction in FPG from baseline at Week 26 between the low-dose treatment regimen and placebo excluding data following rescue medication initiation/early treatment discontinuation

The above primary FPG analysis (Section 4.5.6) for the comparison of mean reduction in FPG from baseline at Week 26 between the low-dose treatment regimen and placebo will be repeated excluding data following rescue medication initiation or early treatment discontinuation, but missing data will be imputed assuming MAR as described in Section 4.1.12.5.

4.5.7 Comparison of the percentage of subjects with baseline HbA1c \geq 7% who achieve an HbA1c level $<$ 7% at Week 26 between overall drug treatment and placebo

Data will be multiply imputed based on the same approach as described for the primary analysis of the primary endpoint in Section 4.4.1, and will include all data regardless of rescue medication initiation or adherence. HbA1c response ($<$ 7%) will be derived from dichotomising the imputed continuous values of HbA1c.

The proportion of responders (subjects achieving an HbA1c $<$ 7% at Week 26) will be analysed using logistic regression and summarised as described in Section 4.1.10. No weights will be used in the multiple imputation or logistic regression for this analysis.

4.5.7.1 Sensitivity analysis for secondary endpoint of percentage of subjects who achieve an HbA1c level < 7% at Week 26 between overall drug treatment and placebo

The above primary analysis (Section 4.5.7) of the percentage of subjects with baseline HbA1c $\geq 7\%$ who achieve an HbA1c level < 7% at Week 26 between overall drug treatment (low-dose and high-dose) and placebo will be repeated with the difference that subjects with any baseline HbA1c value will be used. A logistic regression model will be used for this analysis.

4.5.7.2 Metformin subgroup analysis for comparison of percentage of subjects with baseline HbA1c $\geq 7\%$ who achieve an HbA1c level < 7% at Week 26 between overall drug treatment and placebo

The logistic regression model used for the primary analysis (Section 4.5.7) of the percentage of subjects with baseline HbA1c $\geq 7\%$ who achieve an HbA1c level < 7% at Week 26 between overall drug treatment (low-dose and high-dose) and placebo will also be repeated for the subgroup of subjects on a stable baseline dose of metformin IR or XR (with or without insulin). The same multiple imputation method used for the primary analysis of the endpoint will be used for this subgroup analysis. The indicator for background medication used in the multiple imputation step for insulin only and insulin with metformin will be grouped as defined in Section 4.1.12.

4.5.8 Comparison of the percentage of subjects with baseline HbA1c $\geq 7\%$ who achieve an HbA1c level < 7% at Week 26 between the low-dose/high-dose treatment regimen and placebo

Data will be multiply imputed based on the same approach as described for the primary analysis of the primary endpoint in Section 4.4.1, and will include all data regardless of rescue medication initiation or adherence. HbA1c response (< 7%) will be derived from dichotomising the imputed continuous values of HbA1c and Rubin's rules will be used to combine analyses across the multiple imputations. Estimates will be derived from a weighted logistic regression or Fisher's exact test (as appropriate) and combined as described in Section 4.1.12.4. The weight matrix W1 (described in Section 4.1.9) for the comparison of the low-dose/high-dose treatment regimen versus placebo will be used for this analysis.

4.5.8.1 Sensitivity analysis for secondary endpoint of percentage of subjects who achieve an HbA1c level < 7% at Week 26 between the low-dose/high-dose treatment regimen and placebo

The above primary analysis (Section 4.5.8) of percentage of subjects with baseline HbA1c $\geq 7\%$ who achieve an HbA1c level < 7% at Week 26 between the low-dose/high-dose treatment regimen and placebo will be repeated with no restriction on baseline HbA1c values. A weighted logistic model will be used for this analysis.

4.5.8.2 Metformin subgroup analysis for comparison of percentage of subjects with baseline HbA1c \geq 7% who achieve an HbA1c level $<$ 7% at Week 26 between the low-dose/high-dose treatment regimen and placebo

The weighted logistic regression model used for the primary analysis (Section 4.5.8) of the percentage of subjects with baseline HbA1c \geq 7% who achieve an HbA1c level $<$ 7% at Week 26 between the low-dose/high-dose treatment regimen and placebo will also be repeated for the subgroup of subjects on a stable baseline dose of metformin IR or XR (with or without insulin). The same multiple imputation method used for the primary analysis of the endpoint will be used for this subgroup analysis. The indicator for background medication used in the multiple imputation step for insulin only and insulin with metformin will be grouped as defined in Section 4.1.12.

4.5.9 Comparison of the percentage of subjects with baseline HbA1c \geq 7% who achieve an HbA1c level $<$ 7% at Week 26 between the low-dose treatment regimen and placebo

Data will be multiply imputed based on the same approach as described for the primary analysis of the primary endpoint in Section 4.4.1, between the low-dose treatment regimen and placebo, and will include all data regardless of rescue medication initiation or adherence. HbA1c response ($<$ 7%) will be derived from dichotomising the imputed continuous values of HbA1c and Rubin's rules will be used to combine analyses across the multiple imputations. Estimates will be derived from logistic regression or Fisher's exact test (as appropriate) and combined as described in Section 4.1.12.4. The weight matrix W2 described in Section 4.1.9 for the comparison of the low-dose treatment regimen versus placebo will be used for this analysis.

4.5.9.1 Sensitivity analysis for secondary endpoint of percentage of subjects who achieve an HbA1c level $<$ 7% at Week 26 between the low-dose treatment regimen and placebo

The above analysis (Section 4.5.9) of percentage of subjects with baseline HbA1c \geq 7% who achieve an HbA1c level $<$ 7% at Week 26 between the low-dose treatment regimen and placebo will be repeated with no restriction on baseline HbA1c values.

4.5.9.2 Metformin subgroup analysis for comparison of percentage of subjects with baseline HbA1c \geq 7% who achieve an HbA1c level $<$ 7% at Week 26 between the low-dose treatment regimen and placebo

The weighted logistic regression model used for the primary analysis (Section 4.5.9) of the percentage of subjects with baseline HbA1c \geq 7% who achieve an HbA1c level $<$ 7% at Week 26 between the low-dose treatment regimen and placebo will also be repeated for the subgroup of subjects on a stable baseline dose of metformin IR or XR (with or without insulin). The same multiple imputation method used for the primary analysis of the endpoint will be used for this subgroup analysis. The indicator for background medication used in the multiple imputation step for insulin only and insulin with metformin will be grouped as defined in Section 4.1.12.

4.5.10 Comparison of mean reduction in HbA1c from baseline at Week 26 between the high-dose and the low-dose in subjects who do not achieve an HbA1c < 7% at Week 12

Analysis will be based on the Up-titration Randomised Subjects Data Set and further restricted to subjects on dapagliflozin (or saxagliptin) who had HbA1c $\geq 7\%$ at Week 12 and will include all data regardless of rescue medication initiation or adherence. Missing data in values of HbA1c at Week 26 will be imputed using the multiple imputation approach described in Section 4.1.12. If the MI-WO method is used, Placebo subjects from the Randomised subjects data set will be used in the imputation models to impute missing values for active treatment subjects in the Up-titration randomised subjects data set.

Change from baseline HbA1c at all scheduled time points up to and including Week 26 will be compared between the subjects who are Up-titration Randomised to remain on the low-dose and the subjects who are up-titration randomised to the high-dose using the ANCOVA model described in Section 4.1.9, without weights. The analysis will be evaluated in each imputed data set and the results will be combined using Rubin's rules as described in Section 4.1.12.4. The indicator for background medication used in the multiple imputation step for insulin only and insulin with metformin will be grouped as defined in Section 4.1.12. No weights will be used in the multiple imputation or ANCOVA for this analysis.

4.5.10.1 Sensitivity analysis for secondary endpoint of mean reduction in HbA1c from baseline at Week 26 between the high-dose and the low-dose in subjects who do not achieve an HbA1c < 7% at Week 12 excluding data following rescue medication initiation/early treatment discontinuation

The above analysis (Section 4.5.10) for the comparison of mean reduction in HbA1c from baseline at Week 26 between the high-dose and the low-dose in subjects who do not achieve an HbA1c < 7% at Week 12 will be repeated excluding data following rescue medication initiation or early treatment discontinuation but missing data will be imputed assuming MAR as described in Section 4.1.12.5. No weights will be used in the multiple imputation or ANCOVA for this analysis.

4.5.10.2 Metformin subgroup analysis for comparison of mean reduction in HbA1c from baseline at Week 26 between the high-dose and the low-dose in subjects who do not achieve an HbA1c < 7% at Week 12

The ANCOVA model used for the primary analysis (Section 4.5.10) of the mean reduction in HbA1c from baseline at Week 26 between the high-dose and the low-dose in subjects who do not achieve an HbA1c < 7% at Week 12 will also be repeated for the subgroup of subjects on a stable baseline dose of metformin IR or XR (with or without insulin). The same multiple imputation method used for the primary analysis of the endpoint will be used for this subgroup analysis. The indicator for background medication used in the multiple imputation step for insulin only and insulin with metformin will be grouped as defined in Section 4.1.12. No weights will be used in the multiple imputation or ANCOVA for this analysis.

4.5.11 Comparison of mean reduction in FPG from baseline at Week 26 between the high-dose and the low-dose in subjects who do not achieve an HbA1c < 7% at Week 12

Analysis will be based on the Up-titration Randomised Subjects Data Set and further restricted to subjects on dapagliflozin (or saxagliptin) who had HbA1c $\geq 7\%$ at Week 12 and will include all data regardless of rescue medication initiation or adherence. Missing data in values of FPG at Week 26 will be imputed using the multiple imputation approach described in Section 4.1.12. If the MI-WO method is used, Placebo subjects from the Randomised subjects data set will be used in the imputation models to impute missing values for active treatment subjects in the Up-titration randomised subjects data set.

Change from baseline FPG at all scheduled time points up to and including Week 26 will be compared between the subjects who are Up-titration Randomised to remain on the low-dose and the subjects who are Up-titration Randomised to the high-dose using the ANCOVA model described in Section 4.1.9, without weights. The analysis will be evaluated in each imputed data set and the results will be combined using Rubin's rules as described in Section 4.1.12.4. No weights will be used in the multiple imputation or ANCOVA for this analysis.

4.5.11.1 Sensitivity analysis for secondary endpoint of mean reduction in FPG from baseline at Week 26 between the high-dose and the low-dose in subjects who do not achieve an HbA1c < 7% at Week 12 excluding data following rescue medication initiation/early treatment discontinuation

The above primary analysis (Section 4.5.11) for the comparison of mean reduction in FPG from baseline at Week 26 between the high-dose and the low-dose in subjects who do not achieve an HbA1c < 7% at Week 12 will be repeated excluding data following rescue medication initiation or early treatment discontinuation but missing data will be imputed assuming MAR as described in Section 4.1.12.5. The indicator for background medication used in the multiple imputation step for insulin only and insulin with metformin will be grouped as defined in Section 4.1.12. No weights will be used in the multiple imputation or ANCOVA for this analysis.

4.5.11.2 Metformin subgroup analysis for comparison of mean reduction in FPG from baseline at Week 26 between the high-dose and the low-dose in subjects who do not achieve an HbA1c < 7% at Week 12

The ANCOVA model used for the primary analysis (Section 4.5.11) of the mean reduction in FPG from baseline at Week 26 between the high-dose and the low-dose in subjects who do not achieve an HbA1c < 7% at Week 12 will also be repeated for the subgroup of subjects on a stable baseline dose of metformin IR or XR (with or without insulin). The same multiple imputation method used for the primary analysis of the endpoint will be used for this subgroup analysis. The indicator for background medication used in the multiple imputation step for insulin only and insulin with metformin will be grouped as defined in Section 4.1.12. No weights will be used in the multiple imputation or ANCOVA for this analysis.

4.5.12 Comparison of the percentage of subjects with baseline HbA1c \geq 7% who achieve an HbA1c level $<$ 7% at Week 26 between the high-dose and the low-dose in subjects who do not achieve an HbA1c $<$ 7% at Week 12

Analysis will be based on the Up-titration Randomised Subjects Data Set, further restricted to subjects on dapagliflozin (or saxagliptin) who had HbA1c \geq 7% at Week 12 and will include all data regardless of rescue medication initiation or adherence. Missing data in values of HbA1c at Week 26 will be imputed using the multiple imputation approach described in Section 4.1.12. If the MI-WO method is used, Placebo subjects from the Randomised subjects data set will be used in the imputation models to impute missing values for active treatment subjects in the Up-titration randomised subjects data set.

HbA1c response ($<$ 7%) will be derived from dichotomising the imputed continuous values of HbA1c. Estimates will be derived from logistic regression or Fisher's exact test (as appropriate) and combined as described in Section 4.1.12.4. No weights will be used in the multiple imputation or logistic regression for this analysis.

4.5.12.1 Metformin subgroup analysis for comparison of the percentage of subjects with baseline HbA1c \geq 7% who achieve an HbA1c level $<$ 7% at Week 26 between the high-dose and the low-dose in subjects who do not achieve an HbA1c $<$ 7% at Week 12

The logistic regression model used for the primary analysis (Section 4.5.12) of the percentage of subjects with baseline HbA1c \geq 7% who achieve an HbA1c level $<$ 7% at Week 26 between the high-dose and the low-dose in subjects who do not achieve an HbA1c $<$ 7% at Week 12 will also be repeated for the subgroup of subjects on a stable baseline dose of metformin IR or XR (with or without insulin). The same multiple imputation method used for the primary analysis of the endpoint will be used for this subgroup analysis. The indicator for background medication used in the multiple imputation step for insulin only and insulin with metformin will be grouped as defined in Section 4.1.12. No weights will be used in the multiple imputation or logistic regression for this analysis.

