Randomised schedules will be generated and kept by the Sponsor or designee. Randomisation will be stratified based on baseline anti-diabetes treatment regimen (stable baseline dose of metformin [IR or XR], a stable baseline dose of insulin, or a stable combination of metformin [IR or XR] and insulin), sex, and age (≥ 10 to < 15 years, ≥ 15 to < 18 years). Each subject will be assigned a unique sequential subject number by the Interactive Web / Voice Response System (IWRS). This subject identifier will be used for identification throughout the study and will not be used for any other participant.

After randomisation, it is expected that at least 50% of subjects will be on a stable baseline dose of metformin, with or without concurrent insulin therapy. At least 30% of total randomised

subjects will be between the ages of 10 and 14 years and at least one third, but no more than two thirds, female subjects.

After the lead-in period, eligible subjects with HbA1c of 6.5% to 10.5% at screening will be randomised (Day 1). A blinded HbA1c assessment will be performed at Week 12. At Week 14, subjects will be up-titration randomised to new treatment assignments, based on the Week 12 HbA1c assessment.

The new treatment assignments from Week 14 will be determined as follows.

- All subjects with Week 12 HbA1c values $< 7\%$ will remain on previously assigned low-dose randomised treatment (blinded dapagliflozin 5 mg, or blinded saxagliptin 2.5 mg, or blinded placebo) after the Week 12 assessment.
- Subjects assigned to the blinded dapagliflozin treatment arm at Day 1 randomisation with Week 12 HbA1c values $\geq 7\%$ (irrespective of whether they were rescued or not prior to Week 12) will be Up-titration Randomised in a 1:1 ratio to continue on the low-dose treatment (blinded dapagliflozin 5 mg) or up-titrate to the high-dose treatment (blinded dapagliflozin 10 mg) after the Week 12 assessment.
- Subjects assigned to the blinded saxagliptin treatment arm at Day 1 randomisation with Week 12 HbA1c values $\geq 7\%$ (irrespective of whether they were rescued or not prior to Week 12) will be Up-titration Randomised in a 1:1 ratio to continue on the low-dose treatment (blinded saxagliptin 2.5 mg) or up-titrate to the high-dose treatment (blinded saxagliptin 5 mg) after the Week 12 assessment.

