2.2.3 Up-titration Randomised Subjects Data Set

The Up-titration Randomised Subjects Data Set will consist of the subset of randomised subjects who are Up-titration Randomised because their HbA1c is greater than or equal to 7% at Week 12 (regardless of rescue medication initiation). This data set will be used for efficacy analysis comparing low-dose and high-dose treatment regimens in subjects who do not achieve glycaemic control (HbA1c < 7%) at Week 12. In analyses of the Up-titration Randomised Subjects Data Set, subjects will be presented in the treatment group to which they were randomised at the second randomisation.

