4.1.1 Definitions

Baseline

Unless stated otherwise, for each subject, baseline value of a parameter (e.g., efficacy laboratory parameter, safety laboratory test, ECG or physical measurement endpoint) is defined as the last assessment on or prior to the date of the first dose of the double-blind study medication in the ST treatment period (Day 1).

If there are multiple assessments with the same date and time, the average value will be used as baseline.

For subjects belonging to the Randomised Withdrawal Subjects Data Set, the withdrawal baseline value for a given parameter is defined as the closest available value on or before the day of first dose in the Randomised Withdrawal period.

Change from baseline

Change from baseline to any Week t in the analysis period (i.e., ST treatment period and ST+LT treatment period) is defined as follows:

$C_{Week\ t} = M_{Week\ t} - M_{baseline}$,
where:

- $C_{Week\ t}$ is the change from baseline at Week t ,
- $M_{Week\ t}$ is the measurement at Week t ,
- $M_{baseline}$ is the measurement at baseline.

The “Week t ” to which a measurement belongs is determined using the conventions described in [Table 8](#) (Section 4.1.6).

Last observation carried forward (LOCF)

A post-baseline missing value will be imputed by the last available non-missing post-baseline or post-withdrawal baseline (as applicable) value. If the first scheduled post-baseline or post-withdrawal baseline value is missing, no imputation will be done.

Day 1 is the date of first dose of study drug in the ST period.

Study day is defined relative to the date of first dose (Day 1) received in ST treatment period, and is calculated as:

- If assessment date is before the date of first dose: assessment date - date of first dose in the ST period (Day 1).
- If assessment date is on or after the date of first dose: assessment date - date of first dose in the ST period (Day 1) + 1.

Treatment response to HbA1c

A treatment responder at Week t is a subject with HbA1c $< 7\%$ at Week t (irrespective of baseline value). HbA1c response at Week t will be derived by dichotomising HbA1c values at Week t (binary variable, set to 1 if HbA1c $< 7\%$ at Week t and 0 if HbA1c $\geq 7\%$ at Week t). Where specified, missing HbA1c responses at Week t will be derived from imputed continuous values of HbA1c for Week t .

Rescue medication initiation

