4.1.9 Weighted analysis of covariance (ANCOVA)

In summaries of primary and secondary efficacy endpoints examining the change from baseline at Week t , an ANCOVA model of the differences between Week t and baseline measurements will be used, controlling for baseline value as a covariate, and treatment group (regimen) and randomisation strata as fixed effects. Only main effects of the randomisation strata will be included in the model. The model will have the following form:

$$D_{t,ijm} = \text{intercept} + \beta [Y_{0,ijm}] + \tau_j + \omega_m + \text{error}_{ijm}$$

where:

- $D_{t,ijm} = Y_{t,ijm} - Y_{0,ijm}$ = the Week t change from baseline of subject i in treatment group j and stratum m .
- $Y_{0,ijm}$ is the baseline measurement of subject i in treatment group j and in strata m ,
- $Y_{t,ijm}$ is the Week t measurement of subject i in treatment group j and in strata m ,
- β is the slope of $D_{t,ijm}$ regressing on the baseline measurement,
- τ_j is the mean effect of treatment group j ,
- ω_m is the mean effect of randomisation stratum m ,
- *Intercept*, β and τ_j are unknown parameters to be estimated from the data.

Weights will be used in the ANCOVA model to test the treatment regimens compared to placebo, $\mathbf{H}_{01}: \tau_{TR1} - \tau_{Pla} = 0$ and $\mathbf{H}_{02}: \tau_{TR2} - \tau_{Pla} = 0$.

The weight matrices to test hypotheses \mathbf{H}_{01} and \mathbf{H}_{02} are denoted by \mathbf{W}_1 and \mathbf{W}_2 respectively, defined as follows:

$$\mathbf{W}_1 = \text{Diag} \begin{bmatrix} \mathbf{1}_{1 \times n} \\ \mathbf{1}_{1 \times rn} \\ \mathbf{2}_{1 \times (1-r)n/2} \\ \mathbf{0}_{1 \times \frac{(1-r)n}{2}} \end{bmatrix} \quad \mathbf{W}_2 = \text{Diag} \begin{bmatrix} \mathbf{1}_{1 \times n} \\ \mathbf{1}_{1 \times rn} \\ \mathbf{0}_{1 \times \frac{(1-r)n}{2}} \\ \mathbf{2}_{1 \times (1-r)n/2} \end{bmatrix}$$

where r is the proportion of response (HbA1c < 7%), n is the number of subjects within an arm, and based on a 1:1:1 randomisation.

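### The high-dose versus low-dose ANCOVA (secondary tests 9 and 10) adjusts for Day 1 but not for the Week 12 value taken before the second randomisation: valid, but less precise than it could be

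*SAP*

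**What the plan says.** SAP 1.2 sets the timing: "At Week 14, subjects will be up-titration randomised to new treatment assignments, based on the Week 12 HbA1c assessment". SAP 2.2.3 defines the data set for the dose comparison as the "subset of randomised subjects who are Up-titration Randomised because their HbA1c is greater than or equal to 7% at Week 12".

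Test 9 (SAP 4.5.10) and test 10 (SAP 4.5.11) both use the common ANCOVA. For HbA1c the high-dose side is "the subjects who are up-titration randomised to the high-dose using the ANCOVA model described in Section 4.1.9, without weights". For FPG the high-dose side is "the subjects who are Up-titration Randomised to the high-dose using the ANCOVA model described in Section 4.1.9, without weights". SAP 4.1.9 describes that model as "controlling for baseline value as a covariate, and treatment group (regimen) and randomisation strata as fixed effects". Under SAP 4.1.1, baseline is the latest value up to the first dose on Day 1.

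For the third randomisation SAP 4.1.1 adds a second reference point: "the withdrawal baseline value for a given parameter is defined as the closest available value on or before the day of first dose" in that period. Nothing similar is defined for the second randomisation.

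Week 12 values do enter the MCMC step (SAP 4.1.12.1) and the MAR imputation (SAP 4.1.12.5). The step that fills missing Week 26 values for active subjects uses strata and Day 1 baseline only, under both the retrieved drop-out and the wash-out method (SAP 4.1.12.2 and 4.1.12.3). Protocol 8.4.2.2 calls for an ANCOVA and lists no covariates for this comparison.

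**The concern.** The outcome is change from Day 1, so it includes about 14 weeks during which both groups took the same dose. Differences between subjects that arose in that time are noise for a dose comparison, and the Week 12 value captures part of them. Because it is measured before the second randomisation, adjusting for it is legitimate.

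These are the smallest groups in the confirmatory sequence and the only comparison of the two doses as randomised. SAP 4.5.1 reports p-values and confidence intervals even after the sequence stops, so narrower intervals would be useful whether or not tests 9 and 10 are formally reached.

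**Working it through.** **The plan's own figure.** With 81 per arm, difference 0.75 and SD 1.7 (SAP 1.3), SE = 1.7 × √(2/81) = 0.267 and 0.75/0.267 = 2.81. Normal-theory power is 80.2%, and the noncentral t with 160 df gives 79.7%. The stated 80% reproduces. No power is stated for tests 9 and 10.

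**Inputs for tests 9 and 10**
- From the documents: 81 per initial arm, 1:1 second randomisation, two-sided 0.05, SD of change 1.7.
- Assumed: 50% to 80% of an arm re-randomised, so 81 × 0.5/2 ≈ 20 to 81 × 0.8/2 ≈ 32 per dose group. The 50% appears only in text that Amendment 06 deleted.
- Assumed: residual SD 1.4 to 1.7.
- Assumed: partial correlation r of Week 12 with Week 26, given baseline and strata, 0.3 to 0.8.

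**Formulas.** The planned model has 7 parameters (intercept, treatment, baseline, sex, age, two for background medication), so SE = SD × √(2/n) with 2n − 7 df. Adding Week 12 multiplies the SD by √(1 − r²) and leaves 2n − 8 df. The expected ratio of SEs is √[(1 − r²)(2n − 7)/(2n − 8)]. Detectable differences are for 80% power by noncentral t.

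Results at SD 1.7 (differences in HbA1c percentage points):

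| Model | SE ratio, n = 20 | SE ratio, n = 32 | Detectable, n = 20 | Detectable, n = 32 |
|---|---|---|---|---|
| As planned | 1 | 1 | 1.55 | 1.21 |
| + Week 12, r = 0.3 | 0.97 | 0.96 | 1.48 | 1.16 |
| + Week 12, r = 0.5 | 0.88 | 0.87 | 1.35 | 1.05 |
| + Week 12, r = 0.7 | 0.73 | 0.72 | 1.11 | 0.87 |
| + Week 12, r = 0.8 | 0.61 | 0.61 | 0.93 | 0.73 |

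Over SD 1.4 to 1.7, the detectable difference falls from 1.28–1.55 to 0.77–1.48 with 20 per group, and from 1.00–1.21 to 0.60–1.16 with 32.

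**Cost if Week 12 carries no information.** At r = 0 the ratio is √(33/32) = 1.016 or √(57/56) = 1.009. The added term pays for itself once r² > 1/(2n − 7), which is r above 0.17 (n = 20) or 0.13 (n = 32).

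**Simulation, complete data** (6,000 trials per setting, SD 1.7)
- Mean SE with 20 per group: 0.57 as planned, then 0.55, 0.50 and 0.35 at r = 0.3, 0.5 and 0.8.
- Mean SE with 32 per group: 0.44 as planned, then 0.42, 0.39 and 0.27.
- Power for an illustrative 0.5-point difference: 0.13–0.14 rises to 0.14–0.28 (20 per group), and 0.20 rises to 0.21–0.44 (32 per group).
- Both models were unbiased and rejected a true null 4.8% to 5.4% of the time.

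**Selection at HbA1c ≥ 7%.** Simulating that selection explicitly, with partial correlations of 0.29, 0.47 and 0.67 among those selected, gave SE ratios of about 0.97, 0.89 and 0.75.

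**Imputation.** With wash-out imputation from baseline, 0% to 20% of Week 26 values missing (assumed) and r of 0.3 to 0.7, the added covariate still cut the SE by about 1% to 28%. The estimate stayed unbiased, with null rejection at or below about 5%. With 20 per group and r = 0.5, one such run showed the reduction shrinking from 12% (none missing) to 8% (10% missing) and 6% (20% missing).

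**The case against.** The strongest reply is that nothing is broken. Adjusting for Day 1 and strata is standard, the SAP uses one covariate set for all its ANCOVA tests, and objectives (c) and (g) ask for reduction from baseline. That is right, and it is why this is a precision point only. Adding a covariate leaves the endpoint unchanged.

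The withdrawal baseline is also weak precedent. It defines a different endpoint that SAP 4.6.3.1 only describes, and it is not a covariate in any efficacy model. That stands. It shows that the SAP reset the reference point for one re-randomisation, and no more.

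The size rests on assumptions. Neither the correlation nor the current share re-randomised is in the documents. Selection at 7% narrows the Week 12 HbA1c range, and insulin rescue between Weeks 12 and 26 could weaken the correlation further. The upper value of 0.8 is therefore optimistic. No figure has been computed for FPG.

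If imputation is left as planned, the analysis model contains a predictor that the final imputation step omits. This shrinks the gain, as shown above, but did not bias the estimate or inflate the error rate in simulation.

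The risk from the visit window is real but small. No HbA1c or FPG is scheduled at Week 14, and slotting takes the value nearest Day 85, so a post-randomisation value labelled Week 12 would need an unscheduled, rescue or displaced visit.

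**Conclusion.** The concern holds as a loss of efficiency, with no bias and no effect on type I error, the primary analysis or the testing order. With complete data the plausible saving in standard error for HbA1c runs from about 3% to 39%. At r = 0.5 it is about 12% to 13%. Missing Week 26 data reduce it, and the worst case is a rise of up to 1.6%.

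The benefit is modest in practice. Test 9 is reached only after the primary and eight secondary tests succeed, and test 10 only after nine. In simulation, power for a 0.5-point dose difference at SD 1.7 stayed below 50% throughout the range examined. The change is still worth making, because the data are already collected and the cost is close to nil.

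**What to change.** In SAP 4.5.10 and 4.5.11, add one covariate beside Day 1 baseline and strata: the last value before the second randomisation.
- **Test 9:** the Week 12 HbA1c that triggered re-randomisation.
- **Test 10:** Week 12 FPG or, if missing, the last earlier FPG (Week 6, otherwise Day 1).
- **Source:** do not take the window-slotted Week 12 value. In SAP Table 9 that window runs to Day 113, past the Week 14 target of Day 99.
- **Visits:** SAP 4.5.10 states "Change from baseline HbA1c at all scheduled time points up to and including Week 26 will be compared", and 4.5.11 does likewise. Use the covariate at Weeks 20 and 26 only, since at Week 12 it would be the outcome.

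Endpoints, data set, test order, imputation and test 11 stay as they are. The sensitivity and metformin-subgroup analyses that repeat these tests inherit the model.

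Optionally, and as a separate matter, a sensitivity analysis of the wash-out method could use only placebo subjects with Week 12 HbA1c of 7% or more as the reference.

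The cost is one sentence in each of two sections and one degree of freedom, with no new data and no subjects lost. Protocol 8.4.2.2 is not contradicted. The change must be fixed before unblinding; after that it could serve only as a supportive analysis.
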